3.0 Outcome Measures/Endpoints

- 3.1 Primary Outcome Measures
- 3.2 Secondary Outcome Measures
- 3.1: Patient pain will be measured by means of a NRS at 4 hours after surgical pelvic organ prolapse repair.
- 3.2: Patient pain will be measured by means of a NRS at 8, 12 and 24 hours after surgical pelvic organ prolapse repair. Total opiate consumption will be measured in MME, obtained from the electronic medical record. Time to first narcotic dose will be measured in hours and minutes. Hospital length of stay will be measured in days, hours and minutes.

Patients receiving an opioid prescription after short stay surgeries have a 44% increased risk of long term opioid use. The first 4-24 hours postoperatively is the time when these prescriptions are provided. With appropriate control of postoperative pain in the first 4-24 hours, patients may be able to be discharge without opiate prescription.

4.0 Eligibility Criteria

4.1 Inclusion Criteria

Version Date: 05/25/2023 Page 6 of 13

List the criteria:

- Age >= 18 years
- Access to cell phone with text messaging capabilities (for same day surgery discharge)
- Patients undergoing pelvic organ prolapse repair with peritoneal access

[figure not shown]
4.2 Exclusion Criteria

List the criteria:

- Bupivacaine allergy
- History of epilepsy or other seizure disorder
- EKG demonstrating asymptomatic sinus bradycardia <40 bpm, symptomatic sinus bradycardia <60 bpm, first degree AV block, second degree AV block, third degree AV block, prolonged QT, atrial fibrillation, supraventricular tachycardia, or myocardial infarction
- Chronic liver disease proved by any ALT or AST elevation greater than 2x upper limit of normal
- Serum bilirubin elevation in excess of 5 mg/dL
- G6PD deficiency
- Weight less than 100 lbs
- Chronic opiate use

5.0 Study Design

This will be a double blinded randomized controlled trial. This is the ideal study design as it will serve the purpose of measuring the effectiveness of an understudied intervention (intraperitoneal Bupivacaine) in the management of postoperative pain. Randomization and blinding will help to reduce bias and better assess cause-effect relationships between the intervention and outcome. This study will be done in conjunction with Investigational Drug Services (IDS), who will manage randomization and blinding according to their division protocols. Covariate to be collected include age, BMI, menopausal status, type of surgical procedure, surgical time, and intraoperative complications (Y/N).

Version Date: 05/25/2023 Page 7 of 13

6.0 Enrollment/Randomization

The patients will present to the office for a preoperative visit. At that appointment, the patient will be screened based on the inclusion and exclusion criteria. Consents will be obtained at that visit by a fellow or faculty in the female pelvic medicine and reconstructive surgery (FPMRS) department.

Alternatively, patients can be screened by scheduled operation date and informed of the study during a preoperative phone call. In these circumstances, patients will be consented on the day of surgery. Consents will be obtained by a fellow or faculty in the FPMRS department.

This study will be done in conjunction with Investigational Drug Services (IDS), who will manage randomization and blinding according to their division protocols. This will be done by means of a randomization log that is provided to IDS by the statistician involved.

Patients will be randomized 1:1 to the two pain strategies using stratified randomization with surgery technique being the strata. Block randomization will be used with blocks of size 4. Randomization lists will be constructed by the study statistician using statistical software.

7.0 Study Procedures

In the study, patients will be randomized to one of two groups. Arm 1 will be participants who receive intraperitoneal bupivacaine and arm 2 will be participants who receive placebo (saline).

All patients involved in the study will be undergoing pelvic organ prolapse surgery with peritoneal access and will receive either 30 mL of 0.25% Bupivacaine or 30 mL of saline by means of intraperitoneal lavage. This will be performed at which point peritoneal access will no longer be available, and the solution will be left in the abdomen upon completion of the procedure.

Preoperatively, patients will receive a standardized pain control regimen of Ibuprofen and Tylenol in accordance with hospital ERAS protocol. Postoperatively, patients will receive standardized pain control regimen of Ibuprofen and Tylenol in accordance with hospital ERAS protocol. Patients can be given as needed narcotics if pain is poorly controlled on the initial regimen.

All patients will have pain scores measured at approximately 4 hours using a NRS following completion of the procedure. All patient will have pain scores measured at approximately 8, 12 and 24 hours by means of text message NRS (in the event of same day surgery discharge) vs inpatient in person NRS (for planned admission), following completion of the procedure, which will be stored directly into REDCap. Time to first narcotic dose will be obtained through the hospital electronic medical record. Hospital length of stay will be obtained through the hospital electronic medical record.

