Bupivacaine vs placebo in patients undergoing bariatric surgical procedures. In this study, 106 patients were assigned to receive intraperitoneal lavage with 50 mL of 0.2% Bupivacaine or the same volume of normal saline during the procedure. Using a VAS, patients postoperative pain was rated at 1, 4, 8 and 24 hours after surgery. This study found statistically significant decreased pain scores and opiate consumption among the Bupivacaine group for the first 24 hours after surgery (19). Studies have also been performed evaluating the use of intraperitoneal Bupivacaine vs Tramadol for management of postoperative pain during same day laparoscopic surgery. In a randomized trial of 90 patients assigned to intraperitoneal Bupivacaine (20 mL at 0.25%), IV tramadol hydrochloride (2 mg/kg), intraperitoneal saline (20 mL) or IV saline (2 mL) appreciated better analgesic outcomes among the Bupivacaine group (21).

Of the local anesthetic options available, Bupivacaine is known to have a longer duration of action compared to its counterparts (22). The maximum dose of Bupivacaine that should be administered is 2.0 mg/kg without epinephrine and 2.5 mg/kg with epinephrine (22). Therefore, the maximum allowable dose of Bupivacaine without epinephrine 0.25% should not exceed 56 mL in a 70 kg patient. While toxicity caused by local anesthesia can have CNS (nausea, vomiting, chills, pupil constriction, tinnitus, nervousness, dizziness, blurred vision, or tremors, followed by drowsiness, convulsions, unconsciousness, and possibly respiratory arrest as noted in the package insert) and CVS (depression of the myocardium, decreased cardiac output, heartblock, hypotension, bradycardia, ventricular arrhythmias, including ventricular tachycardia and ventricular fibrillation, and cardiac arrest as noted in the package insert when high doses or unintentional intravascular injection is administered) manifestations, these formulations have relatively wide safety margins and toxicity only occurs when these thresholds are exceeded (22, 23). One systemic review set out to evaluate the safety profile and systemic levels of local anesthesia following intraperitoneal administration (23). In this review, 415 patients were included, 11 (2.7%) were found to have systemic levels close to or above threshold and no cases of clinical toxicity were observed (23).

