10.0 Data Safety Monitoring

A data safety monitoring board (DSMB) composed of [name] (FPMRS faculty), [name] (FPMRS faculty), [name] (FPMRS faculty) and [name] (FPMRS fellow) will be scheduled to meet every 6 months and review the data for patient safety. This will be monitored as part of the Data Safety Monitoring Plan (DSMP): data quality, subject recruitment, accrual, retention, outcome and adverse event data, assessment of scientific reports or therapeutic development, results of related studies that may impact subject safety, and procedures designed to protect the privacy of subjects.

The purpose of this committee will be to evaluate logistical problems and determine if the study should be stopped. Examples of logistical problems would include enrollment rates, follow up rates, or dropout rates. Reasons to stop the study would include if the objective is met prematurely, if the study gives sufficient data against the premise, if the study is proven to be futile, or if there is high index of suspicion that the intervention is harmful. The DSMB will also advise about study progress and performance, protocol changes, and if additional monitoring is necessary.

Version Date: 05/25/2023 Page 9 of 13

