13.0 Statistical Data Management

Primary and secondary objective data will be collected and stored electronically in one REDCap. The storage location will be backed up automatically every day. Quality assurance steps will include testing of database by study team prior to moving to production mode. The following quality control methods will be used extraction and cleaning of data that will be used for analysis every 6 months.

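### After the lavage the plan schedules only pain scores, so the DSMB's adverse event review has no described collection step behind it

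*Combined protocol and SAP*

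**What the plan says.** Section 7.0 gives 30 mL of 0.25% bupivacaine or saline into the peritoneal cavity, and "the solution will be left in the abdomen upon completion of the procedure". For the first contact it says "All patients will have pain scores measured at approximately 4 hours using a NRS following completion of the procedure"; how that score is collected is not stated. The next sentence covers 8, 12 and 24 hours, by text message after same-day discharge and in person for planned admissions, and ends "following completion of the procedure, which will be stored directly into REDCap". The calendar in section 8.0 shows an NRS at the four times and no safety row.

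Section 1.0 describes the toxicities of the drug. On the nervous system: "While toxicity caused by local anesthesia can have CNS (nausea, vomiting, chills, pupil constriction, tinnitus, nervousness, dizziness, blurred vision, or tremors", progressing to convulsions and worse. On the heart: "depression of the myocardium, decreased cardiac output, heartblock, hypotension, bradycardia, ventricular arrhythmias". It also cites a review of 415 patients given intraperitoneal local anesthetic, in which "11 (2.7%) were found to have systemic levels close to or above threshold and no cases of clinical toxicity were observed".

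Section 9.0 makes the principal investigator the assessor of adverse events and refers reporting to an institutional policy. Section 10.0 has a DSMB meet every 6 months; its remit includes "outcome and adverse event data" and stopping for suspected harm. Section 13.0 says that REDCap holds the data for the primary and secondary objectives, and describes "extraction and cleaning of data that will be used for analysis every 6 months".

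**The concern.** The DSMB is asked to review adverse events and, if need be, stop for harm, but the plan does not describe how those events are found. Neither objective in section 2.0 concerns safety, section 3.0 has no safety outcome, and section 12.0 has no safety analysis.

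If the plan is followed as written, the safety data are whatever patients or staff happen to volunteer. Several of the named symptoms, such as nausea, dizziness and drowsiness, are non-specific after surgery. Only a comparison with saline can interpret them, and that needs the same question put to both arms. A low count would reassure the DSMB without informing it. Capture is likely to be least complete after same-day discharge, when the only planned contact is a texted pain score.

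**Working it through.** **1. Sections set side by side**

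| Step needed | What the plan provides |
|---|---|
| Toxicities identified | Section 1.0: CNS and cardiovascular lists |
| Asked about after dosing | Sections 7.0 and 8.0: NRS only, at about 4, 8, 12 and 24 h |
| Abstracted from the record | Sections 3.2 and 7.0: MME, time to first narcotic, length of stay; no toxicity item |
| Stored | Section 13.0: primary and secondary objective data; neither is a safety objective |
| Analysed | Section 12.0: no safety analysis |
| Assessed | Section 9.0: principal investigator; no time window or means of finding events |
| Reviewed | Section 10.0: DSMB, every 6 months |

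The first step and the last two are present. The steps that connect them are not. The intraoperative complication indicator (sections 5.0 and 12.0) stops at the end of surgery.

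**2. Would a better adverse event definition close the gap?** No. Section 9.0 turns on events unexpected in nature, severity or frequency. The toxicities in section 1.0 are already known in nature, so excess frequency becomes a main trigger. Excess frequency cannot be judged without counts sought in the same way in both arms.

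**3. Number exposed.** Section 12.0 gives N = 90, 45 per group. This reproduces: a two-sided t-test with effect size 0.60, alpha 0.05 and 80% power needs 44.6, so 45 per arm (power 80.4%). About 45 patients will therefore receive bupivacaine.

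**4. Dose against the protocol's own limit.** A 0.25% solution contains 2.5 mg/mL, so 30 mL × 2.5 mg/mL = 75 mg. Section 4.2 excludes weight below 100 lb, which is 100 × 0.4536 = 45.4 kg. The largest study dose by weight is 75 / 45.4 = 1.65 mg/kg, below the 2.0 mg/kg without epinephrine given in section 1.0. This counts the study dose alone.

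**5. Prior evidence.** 11/415 = 2.65%, which reproduces the stated 2.7%; this is a rate of systemic levels. For clinical toxicity the count is 0/415, with a one-sided 95% upper bound of 1 − 0.05^(1/415) = 0.72%. If that carried over to this trial, at most about 45 × 0.0072 = 0.3 cases would be expected.

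**6. What zero events here could show.** With every event captured, 0/45 gives an upper bound of 1 − 0.05^(1/45) = 6.4%. If only a fraction s of events is captured, zero captured events bounds the product of s and the true rate at 6.4%, so the bound on the true rate is 6.4%/s. Halving s doubles the bound. With unsolicited reports s is unknown, so no bound follows.

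**The case against.** The strongest reply is that the risk is small and the plan is not silent on safety. The dose is below the protocol's stated limit in every eligible patient, the cited review found no clinical toxicity, the principal investigator assesses adverse events, and a DSMB reviews them. Routine care will observe inpatients, and length of stay from the record would show a prolonged admission, which is one of the seriousness criteria in section 9.0. The institutional reporting policy and the hospital ERAS protocol are not available here. Consent and contact pages were removed before review and may say whom a patient should call. All of this stands, and it lowers the seriousness of the point. None of it describes a safety dataset collected alike in both arms.

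Four stronger readings are tempting, and the documents do not support them.

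- A reader might multiply 2.65% by 45 and expect about 1.2 toxicities. That rate concerns systemic levels close to or above threshold. The same sentence reports no clinical toxicity, and a symptom question cannot detect a blood level.
- A reader might infer that nobody is responsible for patients at home, or that texts go unread for 6 months. Section 9.0 names an assessor, and the 6-monthly step in section 13.0 concerns data for analysis. What is missing is a described route from the patient to that assessor.
- A reader might infer that the seizure and conduction exclusions in section 4.2 were adopted because of these toxicities. The section gives no reasons.
- A reader might want an alert on high texted pain scores. That would add a clinical response triggered by the outcome itself. If bupivacaine works, it would fire more often under saline and could alter later NRS values differently by arm.

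**Conclusion.** The gap in ascertainment is real and should be closed. As written, the DSMB could not tell an absence of toxicity from an absence of enquiry, and its decision on harm would rest on unsolicited reports. The point concerns what the trial can show about safety. It is not a prediction of harm, and it leaves the primary analysis untouched.

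The size is modest. Even perfect collection in 45 exposed patients cannot exclude a toxicity rate below 6.4%; the present plan cannot support even that statement. The conclusion assumes 45 patients treated with bupivacaine and no collection procedure in documents that were not available for review. The judgement that risk is low rests on the study dose alone and on the cited review applying to this dose and setting.

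**What to change.** Reconcile sections 1.0, 7.0, 8.0, 9.0, 10.0 and 13.0 so that each toxicity of interest has a collection step, a place in the database and a route to review:

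- Add a short set of yes/no items, drawn from the symptoms in section 1.0, to the existing 4, 8, 12 and 24 hour contacts, identically in both arms and in both modes (text and in person).
- Abstract recovery-room and inpatient cardiovascular and CNS events from the medical record already used for opioid data.
- Store both in REDCap and list them as safety outcomes, summarised descriptively.
- Tabulate them by arm for each DSMB meeting.
- Name the role that receives symptom reports from patients at home, and say how these reach the principal investigator and the DSMB.

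The choice of items, and any clinical response to an answer, is for the investigators.

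The cost is a slightly longer survey at each contact and some chart abstraction. No new visit is needed. Section 10.0 draws the DSMB from the department whose fellows and faculty obtain consent, so the tables by arm should carry coded labels to protect the blind.

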8.0 Study Calendar

Enrollment Su		4h	8h	12h	24h
---------------	--	----	----	-----	-----

Version Date: 05/25/2023 Page 8 of 13

Consent	Either	Pain assessed	Pain assessed	Pain assessed	Pain assessed
	intervention or	with NRS	with NRS	with NRS	with NRS
	placebo				

9.0 Reportable Events

Adverse Event (AE):

Any medical occurrence in a human study participant, assessed by the principal investigator (PI) that is:

- Unexpected (in terms of nature, severity, or frequency) given the research procedures that are described in the study-related documents, and the characteristics of the subject population being studied
- Related or possibly related to study participation
- Suggests that the research places subject(s) or others at greater risk of harm than was previously known.

Serious Adverse Event (SAE):

- Results in death
- Is life threatening, or places the participant at immediate risk of death from the event as it occurred
- Requires or prolongs hospitalization
- Causes persistent or significant disability or incapacity

AE's and SAE's will be reported as required in accordance with the IU HRPP Policy on Reportable Events..

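### Section 9.0's only adverse event definition reads as a test for an unanticipated problem, so non-serious events that can be called expected may go uncounted and an excess by arm could not be seen

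*Combined protocol and SAP*

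**What the plan says.** Section 9.0 opens its adverse event definition with "Any medical occurrence in a human study participant, assessed by the principal investigator (PI) that is" and then lists three bullets:

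- "Unexpected (in terms of nature, severity, or frequency) given the research procedures that are described in the study-related documents", a test that also takes account of the type of patient under study;
- "Related or possibly related to study participation";
- "Suggests that the research places subject(s) or others at greater risk of harm than was previously known".

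Neither 'and' nor 'or' joins them. A separate list defines a serious adverse event by outcome (for example "Is life threatening, or places the participant at immediate risk of death from the event as it occurred") and sets no condition of expectedness or relatedness. The section ends: "AE's and SAE's will be reported as required in accordance with the IU HRPP Policy on Reportable Events". The text of that policy is not in the documents.

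Section 1.0 lists the known central nervous system effects of local anaesthetic toxicity, starting with "nausea, vomiting, chills, pupil constriction, tinnitus, nervousness, dizziness, blurred vision, or tremors", and known cardiovascular effects that include hypotension and bradycardia. It then states that toxicity arises only above the dose limits it cites.

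Section 10.0 has the DSMB review, among other items, "retention, outcome and adverse event data". Suspected harm is one of its grounds for stopping the study.

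**The concern.** An adverse event definition normally takes in every untoward occurrence and leaves cause and expectedness to be judged afterwards. Here those judgements decide whether an event is counted at all. The three bullets together describe an unanticipated problem. The abbreviation list gives that term its own entry (UP), but the protocol never defines it.

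Nausea, dizziness or low blood pressure after prolapse surgery cannot be attributed with confidence in a single patient. The informative evidence is the comparison of counts between bupivacaine and saline. A case-by-case filter can remove those counts before anyone compares them. The first bullet does admit events of unexpected frequency, but an unexpected frequency cannot be recognised if single occurrences are not recorded. The DSMB would then be asked to judge harm from data that might omit the common non-serious events.

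**Working it through.** **1. Which events the definition admits.** The table applies the Section 9.0 text to five kinds of event.

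| Event | Bullets joint | Bullets as alternatives | SAE list |
|---|---|---|---|
| Non-serious, expected, possibly related | not counted | counted if the PI judges it possibly related | no |
| Non-serious, expected, judged unrelated | not counted | not counted | no |
| Non-serious, unexpected, judged unrelated | not counted | counted | no |
| Non-serious, unexpected, possibly related, suggests added risk | counted | counted | no |
| Meets a seriousness criterion | depends on the bullets | depends on the bullets | captured |

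The joint reading is the natural one: read as alternatives, an unexpected event with no link to the study would qualify by itself. The text does not state it, however. The second row is lost under both readings.

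**2. Whether listed toxicity is 'expected' at the study dose.** Inputs are the 2.0 mg/kg limit without epinephrine (Section 1.0), 30 mL of 0.25% solution (Section 7.0) and exclusion below 100 lb (Section 4.2).

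- 0.25% = 2.5 mg/mL. The plan's own figure reproduces: 2.0 mg/kg × 70 kg = 140 mg, and 140 / 2.5 = 56 mL.
- Study dose: 30 mL × 2.5 mg/mL = 75 mg.
- Lightest eligible patient: 100 lb × 0.4536 = 45.36 kg.
- Highest dose per kg: 75 / 45.36 = 1.65 mg/kg, below 2.0 mg/kg.

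On the protocol's own statement, then, toxicity should not occur at this dose, and a PI could call it unexpected. Yet the same section lists the signs as known effects, and the first bullet allows for what is usual in these patients, so a PI could equally call them expected. Section 1.0 also cites a review in which 11 of 415 patients (11/415 = 2.7%) had systemic levels near or above threshold, none with clinical toxicity. The definition does not settle how one and the same event is classed.

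**3. Whether anything else captures these events.**

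- Section 2.0: no safety objective.
- Section 7.0: after same-day discharge, the planned contact is a text-message pain score.
- Section 8.0: consent, treatment and pain scores only.
- Section 12.0: no adverse event analysis. Intraoperative complications are collected as one yes/no item and compared by arm, but the lavage is given just before peritoneal access is lost, so most of the operation precedes exposure.
- Section 13.0: the data described are those for the primary and secondary objectives.
- No adverse event collection window, grading or symptom list appears anywhere.

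**4. Illustration of size.** The documents give no rates, so these are assumptions. With 45 patients on bupivacaine, a listed non-serious sign at 5% would occur in 45 × 0.05 = 2.25 patients, and at 30% in 45 × 0.30 = 13.5 patients. About 2 to 14 patients could go uncounted. The saline arm would lose its events in the same way.

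**The case against.** The case for leaving the section alone has five parts.

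- **Serious toxicity is covered.** This stands. A reader might infer that every toxicity sign in Section 1.0 could be excluded. The documents do not support that: convulsions, respiratory arrest, ventricular fibrillation or cardiac arrest would enter through the SAE list if life threatening or if they prolonged the stay, and nothing says that an SAE must first meet the three bullets.
- **The bullets may be alternatives.** This is possible. Suspected toxicity would then count whether or not it is expected. What remains is dependence on the PI's view of relatedness, and an ambiguity that the text should remove.
- **Toxicity at this dose is unexpected on the protocol's own terms.** This stands in part. A suspected case could meet all three bullets, so it is too strong to say that the listed effects are expected by definition. The argument is weakest for non-specific signs such as nausea and vomiting.
- **The section concerns reporting and defers to institutional policy.** It may set only a reporting threshold, and Section 10.0 also gives the DSMB a general safety review. That the DSMB sees only events filtered through Section 9.0 is an inference. Even so, no other adverse event definition is given, and the policy is cited for reporting, not for what this trial records.
- **The trial is double-blind, so the PI's judgement should not favour an arm.** This is fair as to bias. But dropping the same share of events in both arms shrinks the difference in counts by that share, and dropping them all leaves nothing to compare.

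**Conclusion.** The point holds for non-serious events that can be judged expected after this surgery or with bupivacaine. Under the joint reading they can be left out of the adverse event data; under the alternative reading their inclusion rests on the PI's view of relatedness. In both cases the documents provide no other planned route by which they would be counted by arm.

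The conclusion rests on two assumptions: that Section 9.0 governs what is recorded, since no other definition is given, and that the unseen policy does not widen it. The size cannot be derived from the documents; the 2 to 14 patients are an illustration at assumed rates.

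A reader might also want to size the problem from a report of no events. If events were sought and none found in 45 patients, the one-sided 95% upper bound would be 1 − 0.05^(1/45) = 6.4%. That describes any true zero in 45 and does not measure this defect. Nor do the documents show that the trial would report none.

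The primary pain analysis is unaffected. The section should be fixed, but this does not undermine the trial's main result.

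**What to change.** In Section 9.0:

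1. Define an adverse event as any untoward medical occurrence after the lavage, within a stated window, regardless of expectedness or relatedness.
2. Record expectedness, relatedness and seriousness as separate fields for each event.
3. Keep the three bullets, joined by an explicit 'and', as the definition of an unanticipated problem for prompt reporting. Leave the SAE list standing on its own.

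In Section 12.0, add a table by arm of the signs that Section 1.0 already lists, taken from the medical record and spontaneous report, and supply it to the DSMB.

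The core cost is protocol wording, a few case report form fields and one table. The downside is more non-serious events to log. Capture will be less complete after same-day discharge unless a symptom question is added to the existing text messages. That is a further data-collection step, worth considering but not needed for the rest of the change.
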